5.0 Analysis Populations

5.1 Definition for Analysis Populations

Seven study populations will be used for analyses in this study. These are:

[figure not shown]
Intent-To-Treat (ITT) population: The ITT population includes all subjects who received at least one dose of the study medication during induction period. ITT subjects will be analyzed as randomized/enrolled.

ITT-E population: The ITT-E population will be a subpopulation of the ITT population, where subjects who have received open-label high induction dose will be excluded. The ITT-E is the primary population for the confirmatory induction period efficacy analyses.

Modified ITT (mITT) population: The mITT population consists of all Week 8 PMS responders who were randomized at Week 8 and received at least one dose of the study medication during maintenance period. mITT subjects will be analyzed as randomized at the beginning of maintenance phase.

mITT-E population: The mITT-E population will be a subpopulation of the mITT population, where subjects who have received Placebo will be excluded. The mITT-E is the primary population for the confirmatory maintenance period efficacy analyses.

Re-Randomized (RR) population: Consists of all subjects who were re-randomized due to a disease flare and received at least one dose of the study medication after the re-

randomization. RR subjects will be analyzed as randomized at the beginning of maintenance phase.

[figure not shown]
Safety population: Includes all subjects who received at least one dose of the study drug. The safety population will be analyzed (separately for induction and maintenance phase) as treated, according to treatment the subject actually received. The safety population will be used for safety analyses.

Per Protocol (PP) populations: The PP populations will only be used for sensitivity analyses of the co-primary and ranked secondary endpoints.

- The I-PP population is a subset of the ITT-E population/mITT-E population consisting of subjects without major protocol deviations within the induction period.
- The M-PP population is a subset of the mITT-E population consisting of subjects without major protocol deviations throughout the study.

The following treatment groups will be distinguished for ITT [ITT-E will comprise only I-HD and I-SD], mITT [mITT-E will comprise only M-HD and M-SD], safety and RR population:

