Non-responder Imputation (NRI): The NRI approach is used for all binary efficacy variables. These variables can take values of 'Response' (i.e., response, remission or mucosal healing) or 'Non-response' (i.e., non-response, non-remission or no mucosal healing) or may be missing for any reason including discontinuation from study. According to the NRI method all missing values will be considered as 'Non-Response'. Subjects re-randomized due to disease flare will be considered as 'Non-Responders' at and after their 1st re-randomization. The confirmatory efficacy analyses will use NRI approach to impute the missing values.

Additionally, only for sensitivity analyses on the mITT population, a **modified NRI** (**mNRI**) approach to impute the missing values will be used. For mNRI method, subjects re randomized due to disease flare will be considered as 'Non-Responders' at and after the switch to the open-label therapy (2nd disease flare).

Last Observation Carried Forward (LOCF): For categorical and continuous efficacy variables the following rules will be used for LOCF approach:

- Baseline and pre-baseline values will not be used to impute the missing post-baseline values, and
- Missing values after baseline will be imputed using the last non-missing values
 after baseline and prior to the missing value. This includes values from
 unscheduled visits and visits where the measurement was not planned to be
 collected per protocol.
- For subjects who were re-randomized due to disease flare, the last non-missing value before or at the re-randomization after 1st disease flare will be carried forward.

[figure not shown]
Unless otherwise noted, for composite scores which consist of several component subscores, components will be imputed first and the composite score will be calculated based on imputed component subscores. Only if composite score still can't be calculated after imputing component subscores, then the previous composite score will be carried forward. The LOCF analysis will only be performed as sensitivity analysis.

Observed Cases (OC): Observed case analysis will be performed on data until 1st re-randomization of subjects with a disease flare. The following rule will be used: missing values will not be used for the observed case analysis. The OC analysis will only be performed as sensitivity analysis.

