9.1 Study Drug Exposure

Induction study drug exposure will be summarized for ITT, ITT-E and safety population by treatment groups defined in Section 5.1. The study drug exposure during induction period does not include the dose received at Week 8. The duration of exposure during induction period will be calculated as follows:

Duration of induction-exposure = last induction dose date - first induction dose date + (max.*) 14 days

*cutting before first dose of study drug in the maintenance period.

Maintenance study drug exposure will be summarized for mITT, mITT-E, RR and safety population (restricted to subjects who received at least one dose of the study drug during maintenance phase). Of note, patients in this study don't receive study drug at Week 52, unless they roll over into Study M10-870, then this will be their first dose of study drug in Study M10-870 (and will be documented in Study M10-870, not Study M11-290). The duration of exposure during maintenance will be calculated as follows:

Duration of maintenance-exposure = last maintenance dose date (prior to potential re-randomization due to 1st disease flare) – first maintenance dose date + (max.*) 14 days

*cutting before first dose of study drug after re-randomization due to 1st disease flare, if applicable, or the first dose of study drug in Study M10-870, if applicable.

[figure not shown]
ADA exposure after re-randomization due to 1st disease flare for the RR population will be calculated as follows:

Duration of ADA exposure after 1st disease flare = last adalimumab dose date in the study after re-randomization due to 1st disease flare – first dose date of adalimumab after re-randomization due to 1st disease flare + (max.*) 14 days

*cutting before first dose of study drug in Study M10-870, if applicable

The overall adalimumab exposure (regardless of double-blind or open-label treatment or if it was rescue therapy after disease flare) will be summarized for the safety population. The duration of overall exposure will be calculated as follows:

- Subjects who are randomized to placebo at Week 8 and who have not been re-randomized due to a disease flare:
 - Overall ADA exposure = Duration of induction-exposure
- Subjects who are randomized to placebo at Week 8 and are re-randomized due to at least one disease flare during maintenance:

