10.0 Efficacy Analysis

10.1 General Considerations

Efficacy analyses will be performed on the ITT population for the Week 8 efficacy endpoints and on the mITT population for the Week 52 efficacy endpoints, unless otherwise noted. Confirmatory analyses will be restricted to ITT-E and mITT-E.

Endpoints that are of the binary type will be analyzed as proportions by treatment group (as defined in Section 5.1) including 95% CIs. NRI (see Section 6.0) will be used, unless otherwise noted. Endpoints that are of the continuous type will be analyzed as changes from baseline, and reported by treatment group (as defined in Section 5.1) including 95% CIs. LOCF (see Section 6.0) will be used, unless otherwise noted.

[figure not shown]
Confirmatory testing of the co-primary and ranked secondary endpoints will be done on the ITT-E (for Week 8 efficacy endpoints) and mITT-E population (for Week 52 efficacy endpoints), where adalimumab dose groups will be tested against external placebo (see Section 10.2) in a sequentially rejective multiple test procedure in order to ensure that the familywise Type I error (multiple significance level) of 5% is controlled in a strong sense, using one-sample two-sided Chi-square tests. The below graph describes the structure of the multiple test procedure that starts with testing the co-primary endpoints for the

[figure not shown]
combined high and standard adalimumab dose groups versus external placebo and then testing individual dose groups versus external placebo separately, as in the figure below.

The results from the test procedure will be displayed also graphically using R.

Multiple Test Procedure for the Co-Primary and Ranked Secondary Endpoints

Assuming ε = 0.0005; C = testing the endpoint for the combined high and standard adalimumab dose groups against external placebo; HD = testing the endpoint for the high adalimumab dose against external placebo; SD = testing the endpoint for the standard adalimumab dose against external placebo; P_1 = co-primary induction endpoint; P_2 = co-primary maintenance endpoint; P_3 = ranked secondary endpoint i (i = 1,...,4)

[figure not shown]

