- Change from Baseline in number of daily stool (last non-missing value prior to the respective visit) over time;
- Change from Baseline in albumin and total protein over time;
- Change from Baseline in hemoglobin, hematocrit, red blood cell count over time;
- Change from Baseline in hs-CRP levels over time;
- Proportion of subjects with EIM at Baseline, Week 26 and Week 52 (OC analysis);
- Proportion of subjects with Mayo endoscopy subscore of 0 or 1 (without friability) at Week 52;

[figure not shown]
- Proportion of subjects being hospitalized (all cause) during the study (OC analysis);
- Proportion of subjects being hospitalized (UC-related) during the study (OC analysis);
- Proportion of subjects undergoing colectomy during the study (OC analysis);
- Proportion of subjects receiving systemic corticosteroids at Baseline who have discontinued systemic corticosteroids prior to Week 52* and completed the study (Week 52) (OC analysis);
- Correlation between PMS and PUCAI at different time points;
- Proportion of subjects in a 9 point Mayo (without SFS) clinical remission (defined as ≤ 2 and no individual subscore > 1) at Week 52 in Week 8 responders per PMS;
- Proportion of subjects in a 9 point Mayo (without PGA) clinical remission (defined as ≤ 2 and no individual subscore > 1) at Week 52 in Week 8 responders per PMS;
- Proportion of subjects in a 9 point Mayo (without RBS) clinical remission (defined as ≤ 2 and no individual subscore > 1) at Week 52 in Week 8 responders per PMS;
- Proportion of subjects in a 6 point Mayo (without SFS and endoscopy subscore) clinical remission (defined as ≤ 1) at Week 8;
- Proportion of subjects in a 6 point Mayo (without PGA and endoscopy subscore) clinical remission (defined as ≤ 1) at Week 8;
- Proportion of subjects in a 6 point Mayo (without RBS and endoscopy subscore) clinical remission (defined as ≤ 1) at Week 8;
- Change from Baseline in Mayo score at Week 52;
- Change from Baseline in PMS over time;
- Change from Baseline in PUCAI over time;
- Change from Baseline in endoscopy subscore at Week 52;
- Change from Baseline in SFS over time;
- Change from Baseline in RBS over time;
- Change from Baseline in PGA over time.

*discontinued systemic corticosteroids prior to Week 52: stop date of corticosteroid must be before the min (nominal day of Week 52 per Visit Window table, visit date at which the endpoint was measured).

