10.7 Efficacy Subgroup Analysis

The subgroups listed below will be used for analysis of co-primary and ranked secondary endpoints including calculation of 95% CIs.

- Sex (male, female)
- Age ($< 13 \text{ years}, \ge 13 \text{ years}$)
- Ethnicity (white, non-white)
- Geographic region (North America, Western Europe, Eastern Europe)
- Disease severity per Baseline Mayo Score* $(\le 9, \ge 9)$
- Prior exposure to anti-TNF* (yes, no)
- Baseline systemic corticosteroid use* (yes, no)
- Baseline IMM use (yes, no)
- Weight ($< 40 \text{ kg}, \ge 40 \text{ kg}$)
- Pancolitis (yes, no)

- Disease duration (≤ Baseline-median, > Baseline-median)
- Baseline hs-CRP (≤ Baseline-median, > Baseline-median)
- Fecal calprotectin (\leq Baseline-median, \rightarrow Baseline-median)
- Induction treatment group* (I-HD, I-SD, I-HD-OL) [only for Mayo clinical remission at Week 52 in the mITT population]
- Week 8 remission status per PMS* (yes, no) [only for Mayo clinical remission at Week 52 in the mITT population]

*the true information from EDC to be used and a footnote to be added for cases where these values are discrepant to the values from IRT.

For the RR population Mayo clinical response and remission at Week 52 by treatment groups with vs. without re-induction dose after disease flare (as defined in Section 5.1) will also be summarized.

[figure not shown]

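### The SAP's default non-responder rule makes the Week 52 efficacy table for re-randomised subjects 0/n in every group, whatever is observed

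*SAP*

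**What the plan says.** The last sentence of SAP 10.7 plans the summary: "For the RR population Mayo clinical response and remission at Week 52 by treatment groups with vs. without re-induction dose after disease flare". It refers to SAP 5.1 for the groups and gives no imputation or data rule.

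The other pieces are elsewhere in the SAP:

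- **Population (5.1).** Entry to the RR population depends on the flare re-randomisation and on a dose given later: "Consists of all subjects who were re-randomized due to a disease flare and received at least one dose of the study medication after the" (quoted up to its final word).
- **Default for binary endpoints (10.1).** "NRI (see Section 6.0) will be used, unless otherwise noted".
- **What NRI does after a flare (6.0).** "Subjects re-randomized due to disease flare will be considered as 'Non-Responders' at and after their 1st re-randomization".
- **The alternative, mNRI (6.0).** It moves the failure point to the switch to open-label treatment at the second flare, but is to be used "only for sensitivity analyses on the mITT population".
- **Observed cases, OC (6.0).** "Observed case analysis will be performed on data until 1st re-randomization of subjects with a disease flare".

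Where the SAP departs from NRI for a binary endpoint, it marks this in the text. An example from 10.4 is "Proportion of subjects undergoing colectomy during the study (OC analysis").

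**The concern.** The event that admits a subject to the RR population is the same event that NRI treats as failure. Applied as written, the rule sets the outcome before any Week 52 score is read.

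With versus without re-induction is a randomised, blinded contrast, and the 10.7 summary is its only planned readout on an efficacy endpoint. SAP 11.2 reports adverse events after re-randomisation for the same groups, using data from that period. Safety by re-induction group would then stand beside a Mayo table of zeros. A reader could take the zeros to mean that nobody regained response, or that re-induction made no difference, when they only reflect the coding. If the rule were instead chosen once results by group were visible, the summary would no longer be pre-specified.

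**Working it through.** The documents give no figure for this table, so there is none to reproduce. The check applies the rules to every possible Week 52 state.

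**1. Groups.** SAP 5.1 splits each maintenance arm (M-HD, M-SD, M-PL) into with re-induction (F-REIND) and without (F-NREIND): 3 × 2 = 6 groups.

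**2. Timing.** RR membership requires a dose after re-randomisation. SAP 9.1 says patients do not "receive study drug at Week 52, unless they roll over into Study M10-870", and in that case the dose belongs to the extension study. Re-randomisation and the dose that follows it therefore precede the Week 52 assessment. NRI applies both at and after re-randomisation, so a same-day assessment would not escape it.

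**3. NRI.** For an RR subject with Week 52 outcome *x* in {response, non-response, missing}, the coded value is non-response in all three cases. The count is 0 of n in each of the 6 groups, for both endpoints and any n. The with-minus-without difference is 0/n₁ − 0/n₂ = 0. Pooling the arms into two groups changes nothing.

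**4. How the output would look.** SAP 10.1 attaches 95% CIs to binary endpoints. RR group sizes are not given and the SAP names no interval method, so this is an illustration only. With the exact interval, the upper limit for 0/n is 1 − 0.025^(1/n):

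| Assumed n per group | Upper 95% limit |
|---|---|
| 3 | 70.8% |
| 5 | 52.2% |
| 10 | 30.8% |
| 15 | 21.8% |

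These would look like ordinary estimates although no outcome data enter them.

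**5. Could another rule in SAP 6.0 supply the table?**

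| Rule | Result for RR subjects at Week 52 |
|---|---|
| NRI (default) | Always non-response |
| OC | No data: observation ends at the first re-randomisation |
| LOCF | Only values up to re-randomisation are carried forward. No Mayo endoscopy is scheduled between screening and Week 52 or early termination |
| MI | Forces non-response after rescue medication, a term the SAP does not define. SAP 4.2 uses rescue for the open-label stage; 9.1 can be read more broadly |
| mNRI | Observed outcome kept unless missing or switched to open-label, so counts can run from 0 to n |

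SAP 6.0 confines OC, LOCF, MI and mNRI to sensitivity analyses. Only mNRI clearly counts responses after the first flare, and its scope is further limited to the mITT population.

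**6. Is mNRI already available?** Week 52 Mayo remission is a co-primary endpoint and Mayo response is the first ranked secondary endpoint. SAP 10.6 plans mNRI for both. mITT includes the former placebo subjects, so it contains the RR subjects, but the mITT groups do not separate them by re-induction.

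**The case against.** The strongest reply is that this is an omission which nobody would carry out literally. A comparison by treatment given after re-randomisation makes sense only with later outcomes, the sponsor probably intended observed data or mNRI, and the fault would show at the first table draft. Intent is likely as described, but the SAP does not state it. It tags exceptions to NRI elsewhere and not here, and the OC tag it uses elsewhere would leave this table empty. SAP 10.6 allows further sensitivity analyses but sets no rule for this table. The March 2020 addendum covers only a Bayesian analysis of the second co-primary endpoint.

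Second, SAP 8.0 reports disposition for the RR groups, including switches to open-label treatment, which require a further flare. That gives indirect evidence by group on persistent disease, so the efficacy picture would not be wholly blank. This stands, but disposition counts are not Mayo response or remission.

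Third, Protocol 8.1.4 counts subjects as failures once they receive rescue therapy in maintenance, which might point the same way as NRI. That rule is written for the ITT-E and mITT analyses, and the protocol describes no RR efficacy summary.

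Fourth, mNRI is not the only sound choice. Observed Week 52 outcomes with missing counted as non-response would also work, and would answer a different question because subjects switched to open-label could still count as responders. This stands too: the essential point is that 10.7 names a rule.

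Finally, the table is descriptive and carries no test. That limits the consequence but does not remove the fault.

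**Conclusion.** The concern holds. Followed as written, the SAP produces 0/n for Week 52 Mayo response and remission in all six RR groups, and a between-group difference of exactly zero, regardless of the data. The result follows from the SAP's definitions and needs no assumption about group sizes or response rates. It rests only on reading NRI as the operative default, since 10.7 notes no exception.

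The reach is one descriptive table. The co-primary and ranked secondary tests are untouched and no collected data are lost. It should still be fixed, because it removes the only planned efficacy comparison of the randomised re-induction groups.

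**What to change.** Add one sentence to SAP 10.7, for example: *The RR summary uses mNRI: a missing Week 52 result, or a move to open-label treatment at the 2nd flare, counts as non-response; the 1st re-randomization does not.*

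In SAP 6.0, extend the mNRI scope with *and for the RR summary in Section 10.7*, leaving the present wording on mITT sensitivity analyses in place.

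If the sponsor prefers observed outcomes with missing as non-response, stating that rule in 10.7, with the same exemption for the first re-randomisation, also repairs the table.

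The cost is one sentence and one phrase. Under the mNRI option no new data or derivation is needed, because 10.6 already calls for mNRI on these subjects and endpoints; the values only have to be tabulated by re-induction group. The confirmatory analyses do not change.

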11.0 Safety Analysis

11.1 General Considerations

Adverse events (AEs), laboratory data and vital signs are the primary safety parameters in this study. Safety analyses will be performed separately for the induction period and the maintenance period by treatment groups (defined in Section 5.1) as well as during overall ADA exposure using the safety population. For maintenance safety summaries, the safety population will be restricted to patients with at least one dose of study drug during maintenance period. The RR population will also be used for selected analyses by treatment groups (defined in Section 5.1).

11.2 Analysis of Adverse Events

Treatment-emergent AEs are defined as events with an onset date after the first dose of the study medication (i.e., on/after Rx Day 1) and with an onset date no more than 70 days after the last dose of the study medication. For subjects who roll over into the extension Study M10-870, the window ends prior to first dose date in Study M10-870 (but not more

than 70 days after the last non-missing injection date in Study M11-290). AEs with missing or unknown severity will be categorized as severe. AEs with missing or unknown relationship to study drug will be categorized as 'Reasonable Possibility' of being related to study drug. AEs that are reported more than 70 days after last dose of study drug will be excluded from the treatment-emergent AE summaries; however, they will be included in a separate AE data listing.

Separate Adverse Event Overview tables of number and percentage of subjects in the safety population with treatment-emergent AEs and events per 100 patient-years of induction-exposure and maintenance-exposure (as defined in Section 9.1) will be provided for events during induction period and events during maintenance period (prior to rerandomization due to disease flare if applicable), respectively. AEs that occur after the first dose of study drug in the maintenance period should not be considered treatment-emergent in the induction period, even if they occurred within 70 days of the last dose of study drug in the induction period.

The Adverse Event Overview tables for treatment-emergent AEs in maintenance period (prior to re-randomization due to disease flare if applicable) will also be provided for the RR population. Additionally, an Adverse Event Overview table of events after rerandomization due to first disease flare per 100 PYs of ADA exposure after first disease flare (as defined in Section 9.1) will be provided for the RR population by treatment groups with vs. without re-induction dose (as defined in Section 5.1).

Additionally, an Adverse Event Overview table of adalimumab-treatment-emergent events (i.e., during any ADA exposure throughout the study) per 100 patient-years of overall ADA exposure (as defined in Section 9.1) for patients in the safety population will be provided.

AEs will also be summarized and presented using primary MedDRA system organ classes (SOCs) and preferred terms (PTs) according to the version of the MedDRA coding dictionary used to code the AE data. The system organ classes will be presented in

Adalimumab M11-290 – Statistical Analysis Plan Version 3.0 – 08 Aug 2019

alphabetical order and the preferred terms will be presented in alphabetical order within each system organ class.

In addition, a summary of AEs by maximum severity and relationship to study drug will be presented.

A subject who reports more than one AE in different system organ classes will be counted only once in the overall total. A subject who reports two or more different preferred terms which are in the same SOC will be counted only once in the SOC total. A subject who reports more than one AE with the same preferred term will be counted only once for that preferred term using the most extreme incident (i.e., most "severe" for the severity tables and as having a 'Reasonable Possibility' of being related to study drug for the relationship tables).

[figure not shown]
Summaries by subject number and listings will also be provided as appropriate.

An overview of AE categories by type of output is provided below:

[figure not shown]
• Adverse Event Overview

The number and percentage of subjects experiencing treatment-emergent AEs, as well as events per 100 PYs, will be summarized for the following AE categories:

- Any AE
- SAEs
- Severe AEs
- AEs leading to discontinuation of study drug
- AEs rated as possibly related to study drug by the investigator (reasonable possibility)
- SAEs rated as possibly related to study drug by the investigator (reasonable possibility)
- AEs leading to Death
- AEs of special interest (see below)

[figure not shown]
- AEs of special interest include:
 - Infections
 - Serious infections
 - Opportunistic infections excluding oral candidiasis and tuberculosis (TB)
 - o TB (active/latent)
 - Oral candidiasis
 - Legionella infections
 - Parasitic infections
 - Diverticulitis
 - Malignancies
 - o Lymphoma
 - Hepatosplenic T-cell lymphoma (HSTCL)
 - o Leukemia
 - Non-melanoma skin cancer (NMSC)
 - Melanoma
 - Malignancy other than lymphoma, HSTCL, leukemia, NMSC or melanoma
 - Lupus-like reactions and systemic lupus erythematosus
 - Allergic reactions including angioedema/anaphylaxis
 - Stevens-Johnson syndrome
 - Sarcoidosis
 - Vasculitis (cutaneous/non-cutaneous)
 - Demyelinating disorder
 - Interstitial lung disease
 - Congestive heart failure (CHF)
 - Myocardial infarction (MI)
 - Cerebrovascular accident (CVA)
 - Intestinal perforation
 - Pancreatitis

- Hematologic disorders including pancytopenia
- Liver failure and other liver events
- o Reactivation of Hepatitis B
- Autoimmune Hepatitis
- Injection site reaction
- o Erythema multiforme
- Worsening or new onset of psoriasis
- Pulmonary embolism
- Progressive multifocal leukoencephalopathy (PML)
- Reversible posterior leukoencephalopathy syndrome (RPLS)
- Amyotrophic lateral sclerosis
- Humira administration related medication error
- Adverse Events by System Organ Class and Preferred Term

The number and percentage of subjects experiencing treatment-emergent AEs, as well as events per 100 PYs, will be summarized by SOC and PT for the following AE categories.

- o Any AE
- o SAEs
- AEs leading to discontinuation of study drug
- Subject Numbers Associated with treatment-emergent Adverse Events by System Organ Class and Preferred Term
 - o Any AE
- Adverse Event listing
 - o Any AE
 - o SAEs
 - Severe AEs
 - AEs leading to discontinuation of study drug
 - AEs rated as possibly related to study drug by the investigator (reasonable possibility)

[figure not shown]
- SAEs rated as possibly related to study drug by the investigator (reasonable possibility)
- AEs leading to Death
- AEs of special interest

